### **Study Design**

We will conduct a single arm, pre / post study with a series of three baseline (Pre-Test) measures, a single post assessment (Post-Test) and a one-week follow up assessment (Follow up). Feasibility measures (in terms of adherence, tolerance and safety) will also be recorded. The availability of feasibility measures is critical for planning future, long-term, randomized controlled trials. Based on prior work, force symmetry can be improved with TPAD training. However, we offer that the integration of a task specific overground training component will

allow individuals to improve transfer of force symmetry into spatiotemporal gait parameters that may ultimately impact gait speed, gait function and quality of life. See Figure 1 for a detailed study schema.

**Figure 1: Trial Schema**

A total of 12 participants will be enrolled to participate. Participants will be assessed over a series of three over ground Pre-Tests by a member of the study team. On completion of over ground Pre Tests, symmetry ratios (paretic/non-paretic limb) will be calculated for percentage of time in stance phase. The mean value of these ratios will be calculated. As the minimal detectable change (MDC) for time in stance has been identified as 0.09, participants will be required to have a mean symmetry ratio of 0.90 or less of time in stance after Day one of Pre Testing to be considered eligible for participation in the trial. Details of other

inclusion/exclusion criteria can be found in the Standard Operating Procedure Manual for this study. The details of data collection are outlined here with an associated plan for statistical analysis.

Following these three visits of Pre-Test assessments, participants will return to complete five consecutive days of the training intervention. The intervention will consist of five consecutive days of TPAD training plus visual feedback training with a short over ground training (5-10 minutes) each day immediately following completion of treadmill based activities. After participants are readied for intervention, they will be assisted onto the treadmill and the treadmill will be initiated. Individuals will self-select gait speed with a physical therapist confirming speed is safe for the duration of training. Once gait speed is set, individuals will initiate five minutes of Baseline gait on the treadmill during which load force measures are recorded at minute 0-1 (BL1), minute 2-3 (BL2) and minute 4-5 (BL3). This Baseline gait will be followed by 40 minutes of tethered TPAD training with visual feedback provided. The amount visual feedback will be faded over the course of the five-day training. On completion of the tethered portion of training, participants will continue to ambulate on the treadmill for an additional 10 minutes during a Post-Training period. Measures of load force will be recorded during minute 0-1 (PT1), minute 3-4 (PT2), minute 6-7 (PT3) and minute 9-10 (PT4) of Post Training. Participants will then be assisted off the treadmill and an additional 5-10 minutes of over ground training will be conducted reinforcing weight shifting onto the paretic limb. Participants will be required to complete at least four days of training for data to be considered in the final analysis. Training sessions will last approximately 60 minutes (one hour) in duration.

On the fifth day of training, immediately following the final training session, participants will be allowed a 10-15 min seated rest break and over ground measures will be reassessed (Post

Test). All participants will be asked to return one week after completion of the intervention to undergo one final over ground assessment (Follow Up).

### **Sample size justification**

This is a pre/post pilot with a one week follow up using multiple baseline (Pre-Test) measures to establish a baseline level of function and variability of gait. Results from this study will be used to calculate sample size for future, larger trials in this population.

### **Study Outcomes**

#### **1. Feasibility**

The primary feasibility outcomes will include an evaluation of safety, tolerance to treatment, and adherence over the course of the trial.

**1.1.** Safety of the intervention will be assessed by recording the number of adverse events (AE) and/or serious adverse events (SAE) that occur throughout the duration of the trial and will be reported as summary data.

**1.2** Treatment tolerance will be measured primarily by rates of perceived exertion (RPE) and secondarily by the percentage of maximum heart rate (HRmax) throughout daily training sessions.

**1.3** Rates of adherence will be presented as a proportion of visits attended out of the total study visits. Participants who are not able to complete at minimum four out of the five training visits (80% adherence) will not be included in the final data analysis.

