METHODS: Participants will undergo a series of three assessments within a one week time frame prior to initiating intervention. Intervention using the TPAD and overground training will occur the following week for five consecutive visits. On completion of the final training visit, participants will be re-assessed, and return for a single follow up visit the next week for the final assessment. Each study visit will be approximately 1-1.5 hours in duration, and total participation should be completed within three weeks.

EXPECTED OUTCOMES: We anticipate this training paradigm will prove feasible in reducing both load and stance asymmetry in a population of individuals with chronic stroke.

II. Research Questions:

- 1) Is a five day gait training program using the TPAD and incorporating augmented visual feedback and an overground walking component feasible in terms of safety, treatment tolerance, and adherence in individuals with chronic stroke who present with gait asymmetry?
- 2) Is this training program effective at improving load force symmetry after five sessions?
- 3) Is this training program effective at improving stance time symmetry in overground gait?

III. Study Design/Methodology

This is a single arm, non-randomized pilot study of feasibility. The study population and details of study procedures are specified below.

IV. Outcome Measures

A. Primary Outcomes

- Measures of Feasibility
 - Safety
 - Adverse Events / Serious Adverse Events
 - Adherence
 - Attendance Rates of Study Visits
 - Tolerance
 - Ratings of Perceived Exertion (RPE)
 - Heart Rate (HR)
- Efficacy
 - Overall Load Force Symmetry (over the course of training)
 - Stance Time Symmetry

B. Secondary Outcomes

- Daily Load Force Symmetry (intraday changes in load force)
- Time in Double Support
- Swing Time Symmetry
- Stride Length Symmetry
- Stride Velocity Symmetry
- Gait Velocity
- Balance (as per the Berg Balance Scale)

V. Study Population

A total of 12 adults (ages 18-75) will be recruited for participation from a voluntary stroke registry, anticipating 20% attrition, or that at least 10 participants will meet criteria and complete study participation.

Inclusion Criteria:

- Chronic (>6 months) stages post stroke
- History of a single stroke event (either ischemic or hemorrhagic by origin)
- Minimal score of 22 or higher on the MoCA
- Must be independent community ambulator (with/without AFO)
- May use a unilateral assistive device (cane, quad cane)

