During this time vertical forces (F_z) will be taken for each the paretic and non paretic limb.

- t.** Video recordings will be made from a posterior view during minutes 5 of post training.
- u.** On completion of post training, participants will be assisted off of the treadmill and reflective markers, safety harness, pelvic belt and arm sling will be removed.
- v.** HR and RPE will be taken and recorded on CRF_TPAD_Form_02 (See attached).

3. Overground Training

- a. Participants will then initiate overground training for which they will ambulate in a quiet corridor and will receive verbal and gentle tactile cues to reinforce TPAD training. Overground training will be between 5-10 minutes. Duration of overground training period will be recorded.
 - Verbal cues will include:
 - “Remember to walk and put as much weight on your right/left (paretic) limb as possible and keep it there as long as possible.”
 - “Can you put more weight on your right/left (paretic) side?”
 - “A little more”
 - “More weight over here”
 - “Keep it/your weight there a little longer with each step.”
 - Tactile cues will include:
 - Gentle tapping at right/left (paretic) side.
 - Gentle tapping at right/left (paretic) quadriceps.
 - Light hand hold around pelvis with gentle weight shift onto paretic side.
- b. On completion of overground training, HR and RPE will be taken and recorded one additional time on CRF_TPAD_Form_02 (See attached).
- c. CRF_TPAD_Form_02 will be completed daily for each intervention session.
- d. Any incidents with patient safety during interventional procedures will be reported on CRF_TPAD_Form_02.
- e. Any missing visits** occurring during intervention will also be noted on CRF_TPAD_Form_02.
- f. This will conclude the training portion of the session.

VII. Participant Withdrawal

Participation in this study is voluntary. Participants will be allowed to withdraw from the study at any point. Withdrawal of participation from this study will not preclude individuals from participating in any future studies relating to stroke or for which the individual would be a potential candidate.

The participant may be withdrawn by a member of the research team if:

- The participant does not complete all Pre-Test Assessments.
- The participant completes < 4/5 training visits
- The participant does not complete Post-Test Assessment
- The participant sustains an injury while participating that would prevent s/he from completing study procedures

VIII. Risk / Benefit

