- Fractures
- Orthopedic related injuries
- Dizziness
- Severe fatigue that requires a ceasing of study procedures

In the case of an adverse event (AE), the participant will be evaluated immediately by the physical therapist present for all study procedures. If the AE persists, study procedures will be stopped, and the study MD notified to evaluate the participant. In such cases where applicable (e.g. fracture, ankle injury) the participant will be referred and assisted to the Emergency Room for immediate attention.

All AEs will be recorded and reported to the PI and IRB within 24 hours.

XI. Statistical Analysis

Please see attached Statistical Analysis Plan.

XII. Dissemination of Results and Publications

Results of this work will be analyzed and a manuscript prepared for publication. Full details of this work including prior work using the TPAD, background, study procedures, statistical analysis procedures and detailed results will be written and stored on file as a part of the final dissertation report.

[name], PT, DPT will serve as primary author on the dissertation with [name], EdD providing sponsorship. [name] will also serve as a primary author for manuscripts prepared discussing the feasibility and preliminary efficacy of the TPAD to reduce asymmetry in a population of individuals after stroke. [name], MS will serve as primary author for any manuscripts detailing technical specifics of implementing TPAD treatment in a population of individuals after stroke. Other participating members of the research team will be recognized in authorship in all manuscripts submitted for publication.

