#### ***2.1.2 Treatment Tolerance***

Group means (SD) of Rate of Perceived Exertion (RPE) over the course of the intervention will be reported summararily for the group. A repeated measures analysis of variance (ANOVA) will be used to determine effect, or change of RPE over the course of the intervention (by day). The percentage of maximum heart rate (HRmax) will also be reported using descriptive measures (mean, standard deviation) for the group, and a repeated measures ANOVA used to assess for change over the course of the intervention.

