#### ***2.1.3 Adherence***

The proportion of adherence to the intervention will be reported descriptively as a percentage of total visits.

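### The 4-of-5 training-visit exclusion is not limited to efficacy: read literally it also filters the primary tolerance results and, on one of two readings, adherence

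*SAP*

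**What the plan says.** SAP, Study Outcomes, 1. Feasibility, names safety, tolerance and adherence as the primary feasibility outcomes. Item 1.3 defines adherence: "Rates of adherence will be presented as a proportion of visits attended out of the total study visits". The next sentence excludes participants "not able to complete at minimum four out of the five training visits (80% adherence) will not be included in the final data analysis". The design text after Figure 1 repeats the rule: "Participants will be required to complete at least four days of training for data to be considered in the final analysis".

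The analysis sections name no population. For tolerance (2.1.2), RPE and percentage of maximum heart rate are summarised for the group, which is not defined, and a repeated measures ANOVA "will be used to determine effect, or change of RPE over the course of the intervention (by day"). For adherence (2.1.3): "The proportion of adherence to the intervention will be reported descriptively as a percentage of total visits". No section defines a feasibility, all-enrolled or per-protocol set.

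Protocol VII allows the team to withdraw someone at the same threshold: "The participant completes < 4/5 training visits". Neither document says whether data collected before such a withdrawal stay in the feasibility results.

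**The concern.** The SAP's Study Objectives make feasibility the chief purpose, and its Study Design section treats the feasibility measures as critical for planning later randomised trials. A rule that keeps only people with at least four sessions selects on adherence. If it governs the adherence result, that outcome is conditioned on itself. If it governs RPE and heart rate, the people who say most about tolerance, those who stopped, leave the record. Someone planning a larger trial from these results might not see that this had happened.

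**Working it through.** **Reach of the rule, outcome by outcome**

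- *Tolerance.* Both statements of the rule are unrestricted, and the opening paragraph of Statistical Analyses lists tolerance among the measures to be tested. Nothing in 2.1.2 takes RPE or heart rate outside the rule, so on a literal reading they fall under it.
- *Adherence.* Two readings are open. The rule sits inside the adherence item, ahead of the Efficacy heading, and 2.1.3 names no one else. Against that, the same opening paragraph omits adherence from the tested measures, and the protocol marks missing visits as a primary outcome in both its assessment and its intervention sections. The references to total study visits say which visits count, not which people.
- *Safety.* Section 2.1.1 covers all related adverse events. Protocol X also counts "Severe fatigue that requires a ceasing of study procedures" as an adverse event, so some early stopping would surface there.

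**Size, if the rule is applied to adherence**

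The plan's own figure reproduces: 4/5 = 80%. That becomes the lowest training adherence any analysed participant can have.

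Inputs from the documents: 5 training visits per person, and 3 Pre-Tests + 5 training visits + 1 Follow Up = 9 study visits (Post Test falls on training Day 5). Twelve people are recruited, "anticipating 20% attrition, or that at least 10 participants will meet criteria and complete study participation". Because that allowance mixes ineligibility with drop-out, the number starting training (n) is taken as 10 or 12.

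Assumed, because the documents give no early-stopping rate: k = 1 or 2 starters stop after s = 1, 2 or 3 sessions, having attended all Pre-Tests and no Follow Up. Everyone else attends everything.

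Training adherence in all starters = [5(n − k) + ks] / 5n.

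| n | k | s = 1 | s = 2 | s = 3 | Reported under the rule |
|---|---|---|---|---|---|
| 12 | 1 | 56/60 = 93.3% | 57/60 = 95.0% | 58/60 = 96.7% | 100% |
| 12 | 2 | 52/60 = 86.7% | 54/60 = 90.0% | 56/60 = 93.3% | 100% |
| 10 | 1 | 46/50 = 92.0% | 47/50 = 94.0% | 48/50 = 96.0% | 100% |
| 10 | 2 | 42/50 = 84.0% | 44/50 = 88.0% | 46/50 = 92.0% | 100% |

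Over all study visits the formula is [9(n − k) + k(3 + s)] / 9n. The lowest value is 80/90 = 88.9% (n = 10, k = 2, s = 1) and the highest is 105/108 = 97.2% (n = 12, k = 1, s = 3).

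The reported 100% follows from assuming perfect attendance by the others. If instead 10 of 12 starters attend exactly four sessions and two stop after s sessions, the rule reports 80.0%. The figure in all starters is (40 + 2s)/60 = 70.0% to 76.7%. With k = 0 there is no bias.

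**Size for RPE**

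If the k stoppers rate Day 1 exertion d points away from the others, leaving them out shifts the Day 1 mean by kd/n. For an assumed |d| = 3 this runs from 3/12 = 0.25 to 6/10 = 0.60 points. The sign is unknown.

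**Interaction with the 15% rule**

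SAP section 5 drops from interpretation any variable with more than 15% of its data missing. With n = 10, k = 2, s = 1, 42 of 50 scheduled sessions are attended, so 8/50 = 16.0% of session-level RPE and heart-rate data would be missing if scheduled sessions are the denominator. Restoring early stoppers without amending section 5 could therefore remove the tolerance outcome altogether.

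**A separate, minor point**

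If the by-day ANOVA is run on people with all five sessions, it selects further. Suppose 12 start, 1 stops after one session, 2 miss one day each and 9 attend all. The 4-of-5 rule keeps 11 people and 45 + 8 = 53 sessions, while a complete-case ANOVA uses 9 people and 45 sessions. The extra loss is 8/53 = 15.1%. The SAP does not state that it will handle missing days this way.

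**The case against.** The best case for the plan is that the authors meant efficacy only. Adherence is to be presented or reported descriptively, not tested; missing visits carry the protocol's primary-outcome mark; and attendance must be counted for everyone before anyone can be excluded. For adherence this is a fair reading, and it stands as one of two. It does not settle the matter, because counting attendance for everyone is not the same as reporting it for everyone.

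It could also be said that the tolerance section carries no 4-of-5 limit of its own, just as the safety section does not. The difference is that safety reporting is worded to cover all related events, while tolerance refers only to an undefined group. The rule still reaches tolerance.

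A reader might infer that the plan has chosen to report adherence only among adherers, or that the feasibility results are bound to be inflated. The documents do not support either. The text is unclear rather than decided for adherence, and the bias exists only if someone falls below four sessions. Every input to the sizes above, apart from the visit counts and numbers recruited, is assumed.

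It is also fair that the ANOVA point does not depend on the 4-of-5 rule and rests on a way of handling missing days that the SAP does not specify.

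**Conclusion.** The concern holds as a defect of scope that should be fixed. The exclusion is unrestricted, it sits in the adherence item, and no feasibility population is named. Literally applied, it removes low adherers from the primary RPE and heart-rate results. For adherence it does so on one of two plausible readings, and the text must say which applies. In the illustration the reported figure would be 100% against 84.0% to 96.7% of training visits. That range rests on the assumed early stopping and on full attendance by everyone else.

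A reader might go further and expect a wrong decision on feasibility. The documents set no numerical feasibility threshold, so the harm is a possibly misleading descriptive primary result and not a wrong pass or fail. Nor do they support extending the point to safety. The direction of any RPE bias is unknown.

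**What to change.** 1. In the design text after Figure 1 and in item 1.3, limit the 4-of-5 exclusion to the efficacy analyses.
2. In 2.1.3, report study-visit adherence for all enrolled participants confirmed eligible, counting visits missed after withdrawal as not attended. Report training-visit adherence for all who start training Day 1. Scoring Pre-Test visits only among Day 1 starters would again select on attendance.
3. In 2.1.2, report RPE and heart rate by day from every attended session of all who start training, with the number of people per day.
4. Report how many completed fewer than four sessions, with reasons, and state that data collected before a withdrawal under Protocol VII are kept. The withdrawal rule itself is unchanged.
5. In SAP section 5, state that sessions not attended because of early stopping do not count towards the 15% rule for adherence, RPE and heart rate.
6. Optional: if the by-day ANOVA uses only people with all five sessions, label it a completer analysis and give its n. A mixed model on all attended sessions is an alternative, not a requirement.

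The cost is a few sentences, since attendance, RPE and heart rate are already recorded on the visit forms. The adherence figure may be less favourable, and n will vary by day.

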#### **2. Efficacy**

There will be two primary measures of preliminary efficacy. First, we aim to establish treatment efficacy on the treadmill. Additionally, we aim to determine whether individuals will

be able to transfer gains to improve symmetry in over ground parameters. Specific outcomes are as follows:

**2.1** The primary outcome measure for efficacy of training on the treadmill will be the calculated load force symmetry ratio as measured load force recorded during Baseline and Post Training on the treadmill with embedded force plates.

**2.2** The primary outcome measure for efficacy of transferability will be the stance symmetry ratio calculated from percentage of time in spent in stance phase of the gait cycle. This will be extracted from data provided by APDM® inertial sensors and measured by the mean of the Pre Test visits to Post Testing.

**2.3** Secondary measures of preliminary force efficacy will include within day changes in load force symmetry as taken on the treadmill. As secondary outcomes to evaluate for transfer of the intervention to overground gait, APDM® inertial sensors will be used to record the percentage of time spent in double support, time in swing phase, stride length, and stride velocity. Symmetry ratios will be calculated for percentage of time in swing phase of the gait cycle, and stride length. Gait velocity as a measure of time performing the 10MWT will also be recorded. Lastly, as an additional balance measure, we will also use the total score of the Berg Balance Scale (BBS).

See Table 1 for a detailed list of measures recorded.

Table 1. All outcome variables and time points at which they will be measured.

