B. Procedures: Conducting the Assessment

- a. Instruct the participant to walk from their current position to the opposing end of the 14-meter path at a 'comfortable pace' on your "GO" signal.
- b. Activate Opal sensors by selecting "Start Recording".
- c. At the sound of the tone, instruct the participant to begin walking.
- d. A stopwatch will be used to capture the 10MWT portion of the pathway.
- e. Times will be recorded on CRF_TPAD_Form 03/03a/03b (See attached).
- f. A member of the study team will walk alongside the participant to ensure safety.
- g. A second member of the study team will video record the participant's gait during performance of the walk using the Sony 6300 camera.
- h. Repeat procedures for all 3 walk trials.
- i. On completion of all 3 trials, the participant will be seated, Opal sensors removed and reattached to the Docking Station.
- j. From tabs (at top of page) select "Power Off Sensors".
- k. Remove sensors from docking station after 'Power Off' sequence is complete.
- l. Ensure Opal sensors go blank.
- m. Detach Docking Station and Access Point from MacBook Pro laptop and replace into APDM® suitcase.
- n. Close Mobility Lab software and shutdown MacBook Pro laptop.

☐ This will complete the gait assessment portion.

2. Balance Assessments

A standardized Berg Balance Scale is performed with each of the participants (CRF_TPAD_Form_04 – See attached).

[figure not shown]
- Assessments will be video recorded, and independent reviewers will score each item of the assessment.
- Total scores will be recorded on CRF_TPAD_Form_03/03a/03b (See attached).

3. Self Assessment

- A Stroke Impact Scale (SIS) will be given to participants to complete on Pre Testing, Day 1, on Post Testing, and on Follow up. Total scores of these assessments will be recorded.

□ This will complete the overground assessment portion.

ii. Treadmill Assessments

- Force Assessments will be recorded on the treadmill in an effort to calculate force symmetry between the affected/less affected limb.

Treadmill assessments will occur simultaneously within the interventional sessions. These assessments will be completed daily during week two of study participation. As they will occur within the intervention, no additional time is needed for data collection during these procedures.

[figure not shown]

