**StrLENSYM**

**StrLENGTH**  
**StrVEL**  
**10MWTIME**

**Assessed at time points 1,2,6,7, and 8 during a series of 3 instrumented 10-meter walk tests.**

Participants will be instrumented with APDM® inertial sensors and perform a series of three, 10-meter walk tests (10MWT). Once sensors are placed, individuals will begin the test in a standing position at one end of a marked 14-meter path. They will be asked to walk to a line at the end of the marked path using the instructions, “*Please walk at a comfortable pace to the line at the other end of the hallway. Do you see the line?*”. A member of the research team will tell the participant when to begin. A 10-meter section at the middle of the path will be labeled. A stopwatch will be used to time the participant during ambulation of the middle 10-meters. Time of ambulation for 10MWT (10MWTIME) will be recorded on paper forms. Other variable data (STANCE, SWING, DS, StrLENSYM, StrLENGTH, StrVEL) will be downloaded in .csv file format from APDM® Mobility Lab software.

Mean values of the three trials will be calculated:

$$\text{Mean} = (10\text{MWT}_{\text{Trial1}} + 10\text{MWT}_{\text{Trial2}} + 10\text{MWT}_{\text{Trial3}})/3$$

Mean values will be reported directly (10MWTIME, DS, StrLENGTH, StrVEL), or used to calculate symmetry ratios.

Symmetry ratios will be calculated from the mean values as follows:

$$\text{STANCE Symmetry Ratio} = (\% \text{ of time in Stance Paretic/Non-Paretic Limb})$$

SWING Symmetry Ratio = (% of time in Swing Paretic/Non-Paretic Limb)  
StrLENSYM Symmetry Ratio = (Stride Length Paretic/Non-Paretic Limb)

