## **Statistical Analyses**

Statistical assumptions and normality will be tested prior to running statistical analysis for measures of treatment tolerance, force symmetry, spatiotemporal gait parameters including stance symmetry and balance. A *p value* of 0.05 or lower will be considered statistically significant for all analyses.

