### ***3.6 Stride Velocity***

Descriptive statistics (Mean (SD)) will be calculated and reported. Mean values of Stride Velocity will be analyzed using repeated measures analysis of variance (ANOVA) to compare to compare the mean of the pre-test measures to measures at post-test and follow up. Bonferonni corrections will be used to control for multiple comparisons. Effect sizes, and 95% confidence intervals will be calculated and reported

with the F/Z statistic and p value. A graphical representation of the data will also be reported. Similar to stance and swing symmetry and double limb support, a linear regression model of daily change over time will be created using change scores from the mean of the three Pre Test measures to Day 1 of training. Within day changes for each of the five training days and changes from daily Pre Testing and from daily Post Testing will also be examined with a regression over time. Results of the regression models will be used to determine the presence of a significant change over the course of the intervention and will be reported with the corresponding slope.

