### ***3.7 Gait Velocity***

Descriptive statistics (Mean (SD)) will be calculated and reported. Mean values of Stride Length Symmetry ratios will be analyzed using repeated measures analysis of variance (ANOVA) to compare to compare the mean of the pre-test measures to measures at post-test and follow up. Bonferonni corrections will be used to control for multiple comparisons. Effect sizes, and 95% confidence intervals will be calculated and reported with the F/Z statistic and p value. A graphical representation of the data will also be reported. Similar to stance and swing symmetry and double limb support, a linear regression model of daily change over time will be created using change scores from the mean of the three Pre Test measures to Day 1 of training. Within day changes for each of the five training days and changes from daily Pre Testing and from daily Post Testing will also be examined with a regression over time. Results of the regression models will be used to determine the presence of a significant change over the course of the intervention and will be reported with the corresponding slope.

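### Gait Velocity is defined as 10 m walk time in seconds, and SAP 3.7 names a different variable, so the plan as written never derives or analyses a walk-test velocity

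*SAP*

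**What the plan says.** - Protocol, IV. Outcome Measures, B. Secondary Outcomes lists "Gait Velocity".
- Protocol, VI.C, gait assessment procedures: "A stopwatch will be used to capture the 10MWT portion of the pathway". The times go onto the case report form.
- SAP, Study Outcomes 2.3: "Gait velocity as a measure of time performing the 10MWT will also be recorded". SAP Table 1, row 11, likewise maps Gait Velocity to the time of the 10MWT. The variable is spelled 10WTIME there and 10MWTIME in 4.2.2.
- SAP 4.2.2 averages the three trials and continues: "Mean values will be reported directly (10MWTIME, DS, StrLENGTH, StrVEL), or used to calculate symmetry ratios". Formulas follow for the three symmetry ratios, but none for distance divided by time.
- SAP, Statistical Analyses 3.7, headed Gait Velocity: "Mean values of Stride Length Symmetry ratios will be analyzed using repeated measures analysis of variance (ANOVA"). Neither 10MWTIME nor a speed appears in that section.
- SAP 3.6, for the sensor-based outcome: "Mean values of Stride Velocity will be analyzed using repeated measures analysis of variance (ANOVA"). Table 1 lists this separately from Gait Velocity (rows 10 and 11).

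**The concern.** There are two linked faults. First, the named outcome and the defined variable are different quantities: velocity is in m/s and rises with improvement, while walk time is in seconds and falls. Second, the section that should say which is analysed names a third quantity, a stride length ratio that already has its own section (3.4). The same sentence recurs in 3.8 Balance, which suggests text carried over from 3.4. An analyst working from 3.7 cannot tell what to analyse.

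The choice of scale has consequences. With about ten completers and no speed limits at entry beyond independent community ambulation, walking ability may vary widely. On the time scale an equal gain in speed counts for much more in a slow walker than in a fast one. The SAP's sample size section also says the results will be used to size later trials. A mean and SD in seconds cannot be turned into a mean and SD in m/s without the individual values.

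**Working it through.** **Inputs from the documents.** Distance 10 m; three trials averaged (SAP 4.2.2). Twelve recruited with 20% attrition and 10 expected to complete (Protocol, Participants); 12 × 0.8 = 9.6, so n = 10 is used below. A p value "of 0.05 or lower will be considered statistically significant for all analyses". SAP 3.7 compares the pre-test mean, post-test and follow-up by repeated measures ANOVA. No power, effect size, SD or speed range is stated for gait velocity, so there is no plan figure to reproduce.

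**Assumptions.** All speeds, gains and SDs below are assumed and shown as ranges.

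**Step 1: does mean time convert back to mean speed?** Time = 10 / speed, for ten evenly spaced walkers.

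- 0.3 to 1.2 m/s: times run from 10/0.3 = 33.3 s to 10/1.2 = 8.3 s. Mean time is 16.03 s, and 10/16.03 = 0.62 m/s. The true mean speed is 0.75 m/s.
- 0.6 to 1.2 m/s: times run from 16.7 s to 8.3 s. Mean time is 11.66 s, and 10/11.66 = 0.86 m/s. The true mean is 0.90 m/s.

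**Step 2: how much weight does the slowest of ten carry?** An equal share is 10%.

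- Share of summed baseline time: 33.3/160.3 = 21% (0.3 to 1.2 m/s); 16.7/116.6 = 14% (0.6 to 1.2 m/s).
- If everyone gains 0.10 m/s over 0.3 to 1.2 m/s, the slowest walker's time falls by 10/0.3 − 10/0.4 = 8.3 s and the fastest's by 10/1.2 − 10/1.3 = 0.6 s. The slowest supplies 33% of the total change. Over 0.6 to 1.2 m/s the share is 19%.
- If everyone gains 10% over 0.3 to 1.2 m/s, the slowest supplies 21% of the change in seconds.

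**Step 3: what happens to power?** Simulation of 20,000 trials per case, n = 10, speeds drawn uniformly over the range, three-occasion repeated measures ANOVA at 0.05. The gain is present at post-test and kept at follow-up. Each occasion has equal error, so the extra precision of averaging three pre-tests is not modelled. Entries are power on time / power on speed.

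| Pattern of change | 0.3–1.2 m/s | 0.4–1.0 m/s | 0.6–1.2 m/s |
|---|---|---|---|
| Equal gain 0.10 m/s, SD 0.10 | 63.6% / 86.0% | 76.8% / 86.1% | 81.5% / 85.9% |
| Equal gain 0.05 m/s, SD 0.06 | 48.2% / 71.0% | 60.2% / 70.8% | 63.8% / 69.8% |
| Proportional gain 10%, proportional error 10% | 77.0% / 76.9% | 79.8% / 79.0% | 81.1% / 79.8% |
| Equal gain 1 s, SD 1 s | 86.2% / 65.4% | 85.8% / 74.7% | 86.0% / 77.7% |

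Against speed, time is 4 to 23 points worse if gains are equal in m/s, within about 1 point if gains are proportional, and 8 to 21 points better if gains are equal in seconds.

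**The case against.** **Using time costs power.** A reader might infer this, but the documents do not support it. They give no power for this outcome and say nothing on how change scales with baseline speed, and the table shows the sign of the difference turning on exactly that.

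**The slowest walker decides the result.** This too can be made to look true. With assumed speeds of 0.25, 0.5, 0.6, 0.7, 0.75, 0.8, 0.85, 0.9, 1.0 and 1.1 m/s and a uniform gain of 0.05 m/s, the slowest supplies 6.67/14.40 = 46% of the change in seconds. With an SD of change of 0.05 m/s, a two-occasion paired t test has 80% power on speed and 30% on time. Those figures rest on one assumed person. Moving only that walker to 0.45 m/s brings the share to 22% and power on time to 66%. One can also build a case where mean speed falls by 0.022 m/s while mean time improves by 0.15 s, but that time change has p = 0.85 and nobody would report it as improvement. Disproportionate weight stands; dominance does not.

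**The plan has safeguards.** In part it does: "Statistical assumptions and normality will be tested prior to running statistical analysis for measures of treatment tolerance, force symmetry, spatiotemporal gait parameters", unusual values are reviewed (SAP section 6), and 3.7 mentions an F/Z statistic, which hints at a rank-based alternative. But no transform or rank test is named for this outcome, the promised check on the influence of outliers covers only primary analyses, and none of this supplies a velocity.

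**Speed is measured elsewhere.** Sensor stride velocity comes from the same walks and is analysed on a velocity scale, so it would be wrong to say the plan contains no speed outcome. It is a separate outcome, however, and does not define Gait Velocity. SAP section 3 does say that gait velocity is recorded on paper forms, but 4.2.2 and the protocol's procedure show that what is written down is the stopwatch time.

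**The outcome is minor.** It is one secondary outcome in a 12-person pilot. That limits the importance of the point but does not answer it.

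**Conclusion.** The point holds as a fault of definition and specification. The protocol names a velocity, the SAP defines a time, no conversion is written, and 3.7 analyses something else. This follows from the text and needs no assumption.

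The numerical consequences do rest on assumed speeds. Mean time understates mean speed by 0.75 − 0.62 = 0.13 m/s for a wide spread and 0.90 − 0.86 = 0.04 m/s for a narrower one. The slowest of ten walkers carries 14% to 21% of summed baseline time, and 19% to 33% of the change under an equal 0.10 m/s gain. No general loss of power can be claimed. Nor can it be said that walk time will be analysed, since 3.7 does not name it. The importance is low, but the correction is worth making because 3.7 has to be edited in any case.

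**What to change.** - SAP 2.3, Table 1 and 4.2.2: define gait velocity as 10 m divided by the stopwatch time for each trial, in m/s, and average the three trial velocities. Use one spelling for the time variable.
- SAP 3.7: replace the stride length symmetry ratio with this velocity, in both the ANOVA and the regressions over training days.
- Report mean walk time descriptively alongside.

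If the team prefers to keep seconds, the alternative is to rename the outcome 10MWT time in both documents, justify the scale, and name that variable in 3.7.

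The cost is one derived column from data already collected. The downside is small but real: if gains are in fact uniform in seconds, analysing velocity loses power (for example 86.2% to 65.4% in the widest assumed range). The scale should therefore be fixed before the data are seen. In return the variable matches its name, and later trials get a mean and SD in m/s.
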